8.3.16 Homeostatic Model Assessment of Insulin Resistance

HOMA-IR is calculated using the following equations:

$$HOMA-IR = \frac{\text{glucose (mg/L)} * \text{insulin(IU/L)}}{405} \text{ or } \frac{\text{glucose (mmol/L)} * \text{insulin(IU/L)}}{22.5}$$

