6.2.2 Formulation, Appearance, Packaging, and Labeling

The drug product is formulated as a tablet containing 50 mg of drug substance and the following inactive ingredients: lactose monohydrate, hydroxypropyl cellulose, sodium lauryl sulfate, microcrystalline cellulose, croscarmellose sodium, colloidal silicon dioxide, magnesium stearate, and Opadry® yellow.

Placebo will be supplied as tablets that look identical to the drug product but contain no drug substance.

Study drug tablets will be supplied in blister cards.

HC tablets for stress dosing will be supplied by the Sponsor in bottles.

In the United States, a 50mg and/or 200 mg of drug substance tablet will be available. The tablets may be packaged into HDPE bottles for use in the open label extension portion of the study.

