8.1.3 Metabolic Assessments

A lipid panel (total cholesterol, low-density lipoprotein [LDL], high-density lipoprotein [HDL], and triglycerides) and hemoglobin A1c (HbA1c), fasting glucose, and fasting insulin will be assessed as part of clinical laboratory (see [Section 13.3](#)). HOMA-IR will be calculated from fasting glucose and fasting insulin. Blood pressure (systolic and diastolic) will be assessed. Body weight, BMI, and WC will be assessed as described in [Section 8.2.3](#).

DXA is a whole-body scan that measures both total body composition (including the mass of fat, bones, and lean tissue) and BMD. One whole-body DXA scan exposes an individual to an effective radiation dose of <10 microSieverts, comparable to the normal background radiation of 1 day at sea level ([Shepherd 2017](#)). DXA scans should be performed for all subjects according to the Schedule of Treatment Period and Follow-up Activities. However, DXA scans will be optional at study centers that lack access to a DXA scanner. The initial DXA scan may be scheduled for any time before the first dose of study drug and will be considered the baseline measurement for the BMD endpoint and body composition assessments. Subjects should not take calcium supplements within the 24 hours before a DXA scan.

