8.3.13 Cardiovascular Risk Factors

CV risk factors are defined by gender in the table below. Subjects with values exceeding the threshold are considered for being at elevated risk for a CV event.

Table 8 CV Risk Factors by Gender

Risk Factor	Female	Male
HOMA-IR ^{1,2,3}	≥ 2.5	≥ 2.5
Waist circumference ^{1,4,5}	≥ 88 cm	≥ 102 cm
Total cholesterol ⁶	≥ 170 mg/dL	≥ 200 mg/dL
LDL cholesterol ⁶	≥ 110 mg/dL	≥ 130 mg/dL
Systolic blood pressure ⁷	≥ 130 mmHg	≥ 130 mmHg
Diastolic blood pressure ⁷	≥ 70 mmHg	≥ 70 mmHg
BMI ⁸	≥ 30 kg/m ² OR ≥ 27 kg/m ² and at least one other risk factor	≥ 30 kg/m ² OR ≥ 27 kg/m ² and at least one other risk factor

1 (Torkey, et al., 2021); 2 (Matthews, et al., 1985); 3 (Muniyappa, Lee, Chen, & MJ, 2008); 4 (Flint, et al., 2010); 5 (WHO, 2008); 6 (Grundy, et al., 2019); 7 (Whelton, et al., 2018); 8 (FDA, 2007)

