8.3.19.2 Total Tildacerfont Dose (mg) Taken

Total tildacerfont dosage (mg) is defined as the dosage of tildacerfont taken over a specific study period i (where subject is receiving a constant dose), calculated as follows:

$Total\ Tildacerfont\ Dose_i$

$$= ((\#Dispensed - \#Returned - \#Lost or Destroyed) \times Tablet\ Strength)_i$$

and total tildacerfont dose over the entire study period is calculated as:

$$Total\ SPR001\ Dose = \sum_{i=1}^k (Total\ SPR001\ Dose)_i$$

where

Σ represents the summation operator and the value in parentheses is summed over the sequence $i = 1$ to k ,

where

k = number of time intervals subject is intended to receive study drug, and Tablet strength is 0 mg if placebo or 200 mg tildacerfont if active drug.

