11 STUDY DRUG AND OTHER MEDICATIONS

11.1 Exposure to Study Drug and Study Treatment Compliance

Summaries of study drug exposure and compliance will be summarized overall and separately for those taken during Placebo-Controlled Treatment Period and the Open-Label Treatment Periods of the study and overall for the Safety Analysis Set and the PP Analysis Set. The source for study drug dosing and compliance is drug accountability.

The summaries will include the total number of doses taken, mean daily dose (mg/day), duration (days) of exposure, and study drug compliance by treatment group.

The drug accountability information, including number of tablets dispensed, number of tablets returned, number of tablets lost or destroyed, and reasons/comments for incomplete or missed doses, along with all summarized variables, will be listed in subject listings. Subject dosing diary information, along with diary compliance, will also be listed in a separate listing.

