12.5.1 Statistical Hypotheses for Secondary Efficacy Endpoints

For Secondary Efficacy Endpoint 2.1 the null hypothesis is that the difference between randomized treatment groups in the proportion of subjects achieving GC dose ≤ 11 mg/m²/day in HCe and A4 ≤ 1.2 times baseline or A4 \leq ULN at Week 24 is equal to zero. The alternative hypothesis is that the difference is not equal to zero.

For Secondary Efficacy Endpoint 2.2 the null hypothesis is that in the subset of subjects with a baseline GC dose ≤ 35 mg the difference between randomized treatment groups in the proportion of subjects achieving GC dose ≤ 11 mg/m²/day in HCe and A4 ≤ 1.2 times baseline or A4 \leq ULN at Week 24 is equal to zero. The alternative hypothesis is that the difference is not equal to zero.

Secondary Efficacy Endpoint 2.3 is the proportion of classic CAH subjects who were randomized into the study who improve at least one baseline CV risk factor at 24 weeks from randomization. This proportion is calculated for each treatment group (e.g., placebo, tildacerfont) as the number of subjects at Week 24 who had at least one CV risk factor at baseline (i.e. subjects without any CV risk factors will not be included in the analysis) and no longer meets one or more of the baselines CV risk factors at Week 24, divided by the total number of subjects in the ITT analysis who were randomized to that specific treatment and had at least one CV risk factor at baseline.

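### As printed, the two HOMA-IR forms in SAP 8.3.16 disagree tenfold and neither fits the 2.5 cut, and SAP 8.3.19.2 assigns 200 mg to a tablet that the protocol describes as 50 mg

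*SAP*

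**What the plan says.** **HOMA-IR.** Protocol 8.1.3 states that "HOMA-IR will be calculated from fasting glucose and fasting insulin". SAP 8.3.16 says "HOMA-IR is calculated using the following equations" and gives two forms joined by an *or*: glucose (mg/L) × insulin (IU/L) / 405, and glucose (mmol/L) × insulin (IU/L) / 22.5.

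SAP 8.3.13, Table 8, lists HOMA-IR of 2.5 or more, in both sexes, as one of seven cardiovascular risk factors, with the explanation "Subjects with values exceeding the threshold are considered for being at elevated risk for a CV event". Secondary endpoint 2.3 is restricted to subjects with at least one such factor at baseline. Under SAP 12.5.1 a responder is a subject who "no longer meets one or more of the baselines CV risk factors at Week 24". Under SAP 9.6, endpoint 2.3 is tested in the Hochberg step once the primary endpoint is met.

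**Exposure.** SAP 8.3.19.2 computes total dose as the net tablet count times tablet strength, where "Tablet strength is 0 mg if placebo or 200 mg tildacerfont if active drug". SAP 8.3.19.3 divides that total by treatment duration to get mean daily dose. SAP 11.1 confirms that accountability counts tablets: "number of tablets dispensed, number of tablets returned, number of tablets lost or destroyed". Protocol 6.2.2 says "The drug product is formulated as a tablet containing 50 mg of drug substance", and the synopsis gives the same 50 mg strength. Protocol 6.2.2 also mentions 50 mg and/or 200 mg tablets for the United States, followed by a sentence on bottle packaging for the open-label extension.

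**The concern.** Two expressions offered as alternatives must give the same answer on the same blood sample, and the result must be on the scale of the threshold applied to it. The HOMA-IR text fails both tests.

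If the derivation is programmed as printed, a subject cannot realistically qualify on HOMA-IR at baseline, and improved insulin resistance cannot count as a response. The effects then spread:

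- Subjects whose only factor is HOMA-IR leave the denominator of endpoint 2.3.
- A BMI of 27 up to 30 counts only alongside another factor, so BMI status can change.
- The baseline number of risk factors, a covariate in the 2.3 model (SAP 12.5.1.1), is undercounted.
- Endpoint 3.5 and the alternative definitions 2.3A to 2.3C inherit the problem.
- Endpoints 3.3 and 3.4, which are changes in HOMA-IR itself, are reported on the wrong scale. Mixing the two forms would add a tenfold inconsistency.

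The exposure rule appears to use the daily dose as the strength of one tablet. That is a wrong strength rather than a wrong unit. It would put a mean daily dose well above 200 mg in the exposure tables of a 200 mg/day trial.

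**Working it through.** **1. Do the two HOMA-IR forms agree?**

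The ratio of divisors is 405 / 22.5 = 18. SAP 13.2, Table 18, equates 3 mmol/L glucose with 54 mg/dL, and 54 / 3 = 18. So the divisors match when the 405 form takes mg/dL. With mg/L the glucose figure is ten times larger, and the first form exceeds the second tenfold whatever the insulin unit. This step uses only the SAP.

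**2. Does insulin in IU/L fit the cut of 2.5?**

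Solve each printed form for the insulin that gives 2.5 at glucose 90 mg/dL (900 mg/L, 5 mmol/L):

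- First form: 2.5 × 405 / 900 = 1.125 IU/L = 1,125 mIU/L.
- Second form: 2.5 × 22.5 / 5 = 11.25 IU/L = 11,250 mIU/L.
- With mg/dL and mIU/L: 2.5 × 405 / 90 = 11.25 mIU/L.

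The documents give no insulin values, so a range must be assumed: insulin 2 to 100 mIU/L, glucose 72 to 300 mg/dL. Results, with the consistent-unit value for comparison:

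| Glucose (mg/dL) | Insulin (mIU/L) | Consistent units | First form | Second form |
|---|---|---|---|---|
| 72 | 2 | 0.356 | 0.00356 | 0.000356 |
| 90 | 10 | 2.22 | 0.022 | 0.0022 |
| 90 | 11.25 | 2.50 | 0.025 | 0.0025 |
| 300 | 100 | 74.07 | 0.74 | 0.074 |

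Against mg/dL and mIU/L, the first form is 100 times too small (×10 for mg/L, ÷1,000 for IU/L) and the second 1,000 times too small. The largest printed-form value in the assumed range is 300 × 10 × 0.100 / 405 = 0.74, below 2.5.

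Both units need correcting. If only insulin were changed to mIU/L, the first form would give 900 × 11.25 / 405 = 25 where 2.5 is meant.

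**3. Exposure**

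Inputs: 200 mg once daily (Protocol 6.1.2), 50 mg per tablet (Protocol 6.2.2), 24 weeks × 7 = 168 days, full compliance.

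- Tablets: 200 / 50 = 4 per day; 4 × 168 = 672.
- SAP rule: 672 × 200 = 134,400 mg; 134,400 / 168 = 800 mg/day.
- At 50 mg: 672 × 50 = 33,600 mg; 33,600 / 168 = 200 mg/day.
- Ratio: 134,400 / 33,600 = 4.

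For a subject taking one 200 mg tablet daily the SAP rule gives 200 mg/day and the ratio is 1. If 25% of treatment days used that tablet, the average would be 0.75 × 800 + 0.25 × 200 = 650 mg/day, a ratio of 3.25. At 50% it would be 500 mg/day, a ratio of 2.5. These shares are assumed.

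Percent compliance (SAP 8.3.19.1) is a ratio of tablet counts and does not use tablet strength.

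**The case against.** The best counter-argument on HOMA-IR is that the printed formula may never be run. SAP 4.3.1.3 lists fasting HOMA-IR among the items assessed through the clinical laboratory, and SAP 4.3.2.5 lists it among the fasting assessments collected. Protocol 8.1.3 says that it is calculated but not by whom. If the laboratory reports the value, the misprint does not reach the data. This stands, and it makes the consequence conditional. It does not repair a formula that the SAP presents as its own derivation.

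A reader might infer that the 2.5 cut can never be met and that no subject has the factor at baseline. The documents do not prove that. The tenfold mismatch follows from the SAP alone, but the further factor of 1,000 rests on an assumed insulin range.

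The equation was also read from a PDF by a program, and the point turns on single characters in the unit symbols. Table 8 keeps mg/dL and Table 18 keeps its micro signs, so loss in conversion is unproven; the source should be checked.

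A reader might also infer that endpoint 2.3 fails. It does not. Six factors remain, several with broad cuts such as diastolic pressure of 70 mmHg or more, and a subject leaves the denominator only if HOMA-IR was the sole factor. The documents give no basis for estimating how many that is. For 3.3 and 3.4, one form used throughout is a constant rescaling, which leaves p-values unchanged though the estimates are wrong.

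On exposure, a reader might infer that every dose summary is four times too large. The packaging sentence in Protocol 6.2.2 does not confine the United States 200 mg tablet to the extension, so the SAP strength is right for anyone who received that tablet in the main study. The error also reaches only descriptive summaries: the adherence criterion of the per-protocol set uses pill counts and diaries, and no efficacy test uses total dose.

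Finally, values this far off would be conspicuous in an output check. That is likely, but SAP section 3 makes the SAP's wording governing and promises pre-specification before unblinding, so the correction belongs in the text.

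**Conclusion.** Both derivations are wrong as printed, to different degrees of certainty.

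- **Established from the SAP alone:** the two HOMA-IR forms differ tenfold, and the 405 form needs mg/dL.
- **Established under the assumed insulin and glucose range:** insulin in IU/L puts both forms below the 2.5 cut, at most 0.74.
- **Conditional on HOMA-IR being derived as printed, under that same range:** the factor drops out of endpoints 2.3 and 3.5, and may alter BMI status and the risk-factor-count covariate. Endpoints 3.3 and 3.4 would be mis-scaled whatever the range. Endpoint 2.3 stays evaluable on six factors, and the primary endpoint is untouched.
- **Exposure:** total and mean daily dose are four times too large for subjects on 50 mg tablets and correct for any subject on the 200 mg tablet. Percent compliance and efficacy tests are unaffected.

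This merits correction before database lock because a multiplicity-controlled endpoint and the exposure tables depend on the text. It is not a reason to doubt the design.

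**What to change.** In SAP 8.3.16, state HOMA-IR as glucose (mg/dL) × insulin (mIU/L) / 405, or glucose (mmol/L) × insulin (mIU/L) / 22.5. Say which form is used, and whether the value is derived or taken from the laboratory.

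In SAP 8.3.19.2, multiply the net tablet count by the labelled strength of the tablets actually dispensed (0 for placebo), and reconcile that section with the protocol synopsis and Protocol 6.2.2. No change of dose is implied.

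The cost is two lines of SAP text. No new data are needed, provided the accountability records identify the strength dispensed wherever the 200 mg tablet was supplied.

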8.3.17 Testicular Adrenal Rest Tumor Volume

For each TART assessment, the total number of TARTs will be captured as well as the size (lesion volume) of each TART individually. The lesion volume for each detectable TART will be calculated as follows using the formula for an ellipsoid (length \times width \times thickness \times 0.52). The total lesion volume for all detectable TARTs will be the endpoint for analysis.

8.3.18 Study Treatment Assignment to Data Records

This study consists of a GC Conversion Period, a two-part Treatment Period (placebo-controlled period and open-label period), and an optional Open-Label Extension Period. For a data record, the planned treatment will be based on a specific study period as follows:

Table 10 Treatment Assignment by Period

Period	Treatment Assignment
GC Conversion Period:	None
Placebo Controlled Treatment Period:	Randomized treatment assignment (placebo or 200 mg tildacerfont QD)
Open-Label Treatment Period:	200 mg tildacerfont QD
Open-Label Extension Period	200 mg tildacerfont QD

The actual study drug treatment will be the study drug a subject was on when a data record was measured/assessed, unless otherwise specified in this section.

8.3.18.1 Actual Treatment for an Adverse Event Record

AEs are those AEs with onset date from the signing of the ICF until the end of the follow up period. No treatment will be assigned to AEs from the initiation of the ICF through the GC Conversion Period AE records.

Treatment emergent adverse events (TEAEs) are those AEs with onset date from the date of first dose of randomized study drug until 30 days after the last dose of study drug. The actual study treatment will be assigned to these records.

If a subject discontinues study drug but remains in the study, AEs with onset date after 30 days of last dose of study drug until the end of the follow up period will be considered post-treatment adverse events. The last treatment that the subject was on before study drug discontinuation will be assigned to these records.

8.3.18.2 Actual Treatment for a Medication Record

Since a medication could be a prior medication and be taken during the GC Conversion Period and/or Treatment Periods, flag variables will be used to identify a medication record that was taken while a subject received placebo or 200 mg tildacerfont. A medication record will be assigned to the first study treatment when the subject was on and was taking the medication during the Treatment Periods.

8.3.19 Study Drug Exposure Variables

8.3.19.1 Study Drug Compliance

Study drug compliance is defined as the percentage of study drug actually taken compared to what was expected based on the randomized dose for time period i (where subject is receiving a constant dose). Using the drug accountability data, study drug compliance is calculated as follows:

$$\%Compliance_i = 100 \times \left(\frac{\# Dispensed - \# Returned - \# Lost or Destroyed}{\# Expected tablets to be taken} \right)_i$$

and total % compliance over a treatment period is calculated as:

$$\%Compliance = 100 \times \left(\frac{\sum_{i=1}^k (\#Dispensed - \#Returned - \#Lost or Destroyed)_i}{\sum_{i=1}^k (\#Expected\ tablets\ to\ be\ taken)_i} \right)$$

where

Σ represents the summation operator and the value in parentheses is summed over the sequence $i = 1$ to k ,

where

k = number of time intervals subject is receiving a constant dose, and possible constant dose levels are placebo or 200 mg QD tildacerfont.

The expected number of tablets to be taken is the number of expected tablets per day, based on the randomized dose, multiplied by the number of days in time period i . Within each time period i , if there is no documented number of returned, lost, or destroyed tablets, a conservative approach to the calculation of compliance will assume all tablets were lost and therefore not taken, resulting in a compliance calculation of zero for the given time period. Compliance over 24 weeks of randomized treatment will be summarized in terms of the proportion of subjects with 100% compliance, ≥ 80 to $<100\%$ compliance, ≥ 50 to $<80\%$ compliance and $<50\%$ compliance.

8.3.19.2 Total Tildacerfont Dose (mg) Taken

Total tildacerfont dosage (mg) is defined as the dosage of tildacerfont taken over a specific study period i (where subject is receiving a constant dose), calculated as follows:

$Total\ Tildacerfont\ Dose_i$

$$= ((\#Dispensed - \#Returned - \#Lost or Destroyed) \times Tablet\ Strength)_i$$

and total tildacerfont dose over the entire study period is calculated as:

$$Total\ SPR001\ Dose = \sum_{i=1}^k (Total\ SPR001\ Dose)_i$$

where

Σ represents the summation operator and the value in parentheses is summed over the sequence $i = 1$ to k ,

where

k = number of time intervals subject is intended to receive study drug, and Tablet strength is 0 mg if placebo or 200 mg tildacerfont if active drug.

8.3.19.3 Mean Daily Tildacerfont Dose (mg/day)

Mean Daily tildacerfont Dose (mg/day) is calculated as Total tildacerfont Dose (mg) divided by Treatment Duration (days) for each study period and over the entire study.

8.3.19.4 Study Drug Exposure Duration (days)

The duration (days) is calculated as (LASTDAY - FIRSTDAY + 1 day), where LASTDAY is the date of last dose during a treatment period, and FIRSTDAY is the date of first dose during the treatment period.

8.3.19.5 Diary Compliance

For daily diary entries that have a double entry on a given day: if the prior day is missing an entry, then the first of the double day entry applies to the previous day. If the prior day is not missing and two entries exist, use last entry for the given date.

8.3.19.5.1 Study Drug Diary Compliance

Total study drug diary compliance is calculated as the total count of 'Yes' responses to taking study drug as directed, divided by (LASTDAY - FIRSTDAY + 1 day), where LASTDAY is the date of last dose, and FIRSTDAY is the date of first dose.

Weekly diary compliance is calculated as the total count of number of 'Yes' responses to taking study drug as directed within the duration {Study Day (7n+1) to Study Day (7[n+1])}, divided by 7. Where n has values {0, 1, 2, ..., 76}. Missing entries are counted as non-compliance.

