7 STUDY DRUG DISCONTINUATION AND PARTICIPANT WITHDRAWAL

7.1 Study Drug Discontinuation

Subjects may voluntarily discontinue study drug at any time. The Investigator and/or Sponsor may also discontinue a subject's study drug at any time. Study drug will be discontinued in subjects who experience individual treatment-stopping criteria described in this section. The Sponsor and Investigator will make efforts (when possible) to continue to collect data (according to the Schedule of Treatment Period and Follow-up Activities) on subjects who discontinue study drug.

When feasible, Investigators should discuss any safety concerns with the Medical Monitor as soon as possible to determine whether a subject should continue or discontinue study drug.

If study drug is discontinued, the Investigator will report the discontinuation to the Medical Monitor, document the date and reason for study drug discontinuation on the appropriate electronic case report form (eCRF), schedule an early termination visit for the subject (see the Schedule of Treatment Period and Follow-up Activities in [Section 1.3.3](#)), provide or arrange for appropriate follow-up, and document the course of the subject's condition.

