9.3 Populations for Analyses

The ITT Population will include all randomized subjects. The ITT Population will be the primary analysis set for analyzing demographics, baseline characteristics, and efficacy.

The mITT Population will include all randomized subjects who receive at least 1 dose of study drug (tildacerfont or placebo).

The PP Population will include all randomized subjects who have no major protocol deviations that would affect the analysis of efficacy data, defined as the following:

- Subject did not meet efficacy-based inclusion criteria (hormone levels, GC regimen)
- Subject met efficacy-based exclusion criteria (inadequate adherence to GC regimen, night-shift worker)
- Subject's adherence to study drug or the subject-specific GC regimen was <80% over the Treatment Period

Additional criteria may be specified in the SAP. The PP Population will be identified prior to database lock.

The mITT and/or PP Populations may be used for secondary analyses of the primary and secondary efficacy endpoints.

The Safety Population will include all subjects who receive at least 1 dose of study drug (tildacerfont or placebo), summarized by actual drug received. The Safety Population will be the primary analysis set for general and safety analyses.

The PK Population will include all subjects who receive at least 1 dose of tildacerfont and have at least 1 evaluable PK sample.

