7.3 Per-Protocol Analysis Set

The Per-Protocol (PP) Analysis Set for each part of the Treatment Period will include all eligible subjects who have no major protocol deviations that would affect the analysis of efficacy data, defined prior to the database lock as the following:

- Subject did not meet efficacy-based inclusion criteria (hormone levels, GC regimen)

- Subject met efficacy-based exclusion criteria (inadequate adherence to GC regimen, night-shift worker)
- Subject's adherence to study drug or the subject-specific GC regimen, determined by pill count and diary data compliance, was < 80% over the Treatment Period
- Subjects having laboratory data specifically hormone levels during stress dosing periods instead of waiting 5 days per protocol.

The PP population will be used for supportive analyses of the Primary and Secondary Efficacy Endpoints only.

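### Total diary compliance stops counting at the last dose, so it does not measure the Per-Protocol rule of 80% adherence over the Treatment Period, and pill count has no stated end after discontinuation

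*SAP*

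**What the plan says.** Protocol 9.3 lists as a PP exclusion: "Subject's adherence to study drug or the subject-specific GC regimen was <80% over the Treatment Period". SAP 7.3 repeats the rule and names the measures, adherence being "determined by pill count and diary data compliance, was < 80% over the Treatment Period". It also says that the PP set is formed separately for each part of the Treatment Period. Neither list includes early discontinuation of study drug or a minimum exposure.

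The SAP defines the measures as follows:

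- **Total study-drug diary compliance (8.3.19.5.1):** days answered Yes, "divided by (LASTDAY - FIRSTDAY + 1 day), where LASTDAY is the date of last dose". The GC version in 8.3.19.5.3 has the same denominator and does not say whether the last dose is of GC or of study drug.
- **Weekly diary compliance (8.3.19.5.1):** a fixed denominator of seven days, with the rule "Missing entries are counted as non-compliance". The PP criterion does not mention the weekly measure.
- **Pill-count compliance (8.3.19.1):** tablets taken over tablets expected, "for time period i (where subject is receiving a constant dose"). Expected tablets per day are "based on the randomized dose, multiplied by the number of days in time period i". The same section plans a table of compliance over the 24 randomized weeks.

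SAP 11.1 names drug accountability as the source for study-drug compliance. SAP 10.2 treats less than 80% by pill count or by e-diary as a major deviation. Protocol 7.1 asks sites, when possible, to "continue to collect data (according to the Schedule of Treatment Period and Follow-up Activities) on subjects who discontinue study drug".

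**The concern.** A denominator that ends at the last dose answers how well a subject adhered while still dosing. The PP rule asks how much of the period's treatment the subject took. For anyone who stops early, the two answers can be far apart.

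The PP analysis of the primary endpoint is the planned analysis that restricts by adherence, and SAP 12.4.1 reports it only at Week 24. If early stoppers count as fully adherent, the set can drop a subject who took 78% of doses through Week 24 and keep one who took 17% and stopped. A kept subject who remains in follow-up brings a Week 24 GC dose set largely after drug was stopped. For a Day 28 stopper, the Week 6, 12 and 18 dose decisions all fall after the stop. In the tildacerfont arm this would tend to dilute the PP contrast and blur its difference from ITT.

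**Working it through.** The documents give no figure that depends on this point, so there is nothing to reproduce. The check applies the SAP formulas to a subject who takes every dose on Days 1 to 28, records each one, and then stops.

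**Inputs.** The placebo-controlled part is 24 weeks, or 24 × 7 = 168 days. The whole Treatment Period is 76 weeks, or 76 × 7 = 532 days. The dose is 200 mg once daily as 50 mg tablets (Protocol 6.2.2), so 4 tablets a day; the ratios do not depend on this number.

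| Measure | Calculation | Result |
|---|---|---|
| Total diary, as written | 28 / (28 − 1 + 1) | 100% |
| Mean weekly diary over 24 weeks | 4 / 24 | 16.7% |
| Pill count, period ends at last dose | (4 × 28) / (4 × 28) = 112/112 | 100% |
| Pill count, period runs to Week 24 | 112 / (4 × 168) = 112/672 | 16.7% |
| Share of planned 24 weeks taken | 28 / 168 | 16.7% |
| Share of all 76 weeks taken | 28 / 532 | 5.3% |

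**Where the 80% line falls.** 0.80 × 168 = 134.4 days. A fully adherent subject who stops on Day 134 has taken 134/168 = 79.8% of the planned doses, and one who stops on Day 135 has taken 135/168 = 80.4%. So any fully adherent subject who stops on or before Day 134 took less than 80% of the plan and scores 100% on the diary formula. By contrast, 131 recorded doses with the last on Day 168 give 131/168 = 78.0%, a fail.

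**PP status of the Day 28 stopper.** SAP 7.3 does not say how the two measures combine; SAP 10.2 says either one suffices. On the SAP 10.2 rule:

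- If pill count also ends at the last dose, both measures give 100% and the subject is kept.
- If pill count runs to Week 24, it gives 16.7% and the subject is excluded.

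**Follow-up.** Days 29 to 168 are 140 days (20 weeks) off drug before the Week 24 visit.

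**Possible size, on an assumption.** The documents give no discontinuation rate. If 10 to 15% of 45 per arm stopped early, that is 4.5 to 6.75, or roughly 4 to 7 per arm. This is an upper bound on those wrongly kept. It requires that all stop by Day 134, adhere well until then, have no other PP deviation, and are scored to the last dose on both measures.

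**The case against.** The strongest reply is that the diary formula is not the study-drug compliance measure. SAP 11.1 gives that role to drug accountability, and the pill-count formula does not refer to the last dose. It compares tablets taken with tablets expected at the randomized dose and is summarized over 24 weeks. Read that way, the Day 28 stopper scores 16.7%, and under SAP 10.2 one failing measure is enough. The PP wording itself refers to the Treatment Period, and the weekly diary measure would also give a low score. If no returned, lost or destroyed tablets are documented, SAP 8.3.19.1 scores that period as zero.

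Much of this stands. It does not follow from the text that an early stopper stays in the PP set, or that the 24-week pill-count table is overstated.

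It does not remove the problem. The total diary formula is explicit and does not deliver the stated criterion. Pill-count periods are tied to receiving a constant dose, with placebo and 200 mg the only levels listed, so ending the period at discontinuation is at least as natural a reading. The early termination visit includes drug accountability, so the zero default would not usually apply. Nothing says that the weekly measure feeds the PP rule.

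The limits on impact also stand. An off-drug Week 24 value exists only if follow-up continues, which the protocol promises only when possible. No figure in the documents gives the size of any dilution, which also depends on GC doses moving back after the drug is stopped.

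**Conclusion.** The SAP's total diary formulas do not match the PP criterion that they are meant to inform. That holds on the text alone: 100% against 16.7% for a fully adherent Day 28 stopper, and the same mismatch for any stop up to Day 134. Whether such a subject is kept in the PP set is unresolved, because the end of the pill-count period and the way the two measures combine are not settled. Retention follows if pill count also ends at the last dose.

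A reader might infer that the plan certainly keeps early stoppers as adherent, or that the main result is at risk. The documents support neither. The first needs a reading of the pill-count period that the SAP leaves open. The second fails because the primary analysis is ITT under a treatment-policy estimand that ignores discontinuation; its sample size and alpha do not depend on compliance. The effect is confined to the supportive PP analyses and the compliance summaries. It is still worth correcting, because PP membership should not depend on a programmer's choice of denominator.

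**What to change.** In SAP 7.3 and 8.3.19:

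1. For the PP adherence rule in the placebo-controlled part, and for the 24-week compliance table, use planned days from first dose to the Week 24 visit (168 if there is no visit) as the denominator for both study-drug pill count and study-drug diary. Count days after permanent discontinuation as not taken.
2. For GC adherence in the PP rule, use the same planned-period denominator.
3. State that less than 80% on either measure excludes the subject, which aligns SAP 7.3 with SAP 10.2.
4. Keep the last-dose denominator only to describe on-treatment exposure.

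Excluding everyone who stops before Week 24 is not an equivalent shortcut. A fully adherent subject who stops on Day 150 has 150/168 = 89.3%, which meets the 80% rule, but such an exclusion would remove that subject.

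The cost is a few lines of text before database lock and no new data. The PP set becomes somewhat smaller.
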